## **12.4 Body Weight**

Body weight will be measured and recorded in pounds or kilograms.

## **12.5 12-lead Electrocardiogram**

A 12-lead ECG will be performed after the subject has rested for at least 5 minutes in a supine position. The ECG must include the following measurements: R wave to R wave (RR) interval, heart rate, QRS, QT, corrected QT interval by Bazett (QTcB), and corrected QT interval by Fridericia (QTcF).

The Investigator will perform an overall evaluation of the ECG for safety purposes and the recording will be reported as 'normal', 'abnormal CS', or 'abnormal NCS'.

Abnormalities of clinical significance will be reported as AEs. Repeat measurements will be performed if needed.

## **12.6 Clinical Laboratory Tests**

The following parameters will be evaluated during the study (refer to Table 1 for further details).

As a guideline, the volume of blood to be collected per time point shall be approximately 8 mL and the volume of urine to be sampled per time point shall be about 10 mL.

### **12.6.1 Hematology**

Red blood cell count, hemoglobin, hematocrit value, white blood cell count including differential, and platelet count.

### **12.6.2 Blood Chemistry**

Albumin, total protein, AST, ALT, lactate dehydrogenase, alkaline phosphatase, total bilirubin, direct bilirubin, creatine kinase, total cholesterol, triglycerides, blood urea nitrogen, bicarbonate, serum glucose, serum creatinine level, uric acid, sodium, potassium, chloride, and calcium.

### **12.6.3 Urinalysis (Qualitative)**

Protein, glucose, occult blood, urobilinogen, white blood cells, and bilirubin.

### **12.6.4 Pregnancy Test**

For female subjects only, serum beta-human chorionic gonadotropin level will be conducted. If the subject tests positive for pregnancy, the subject will be excluded from clinical study.

### **12.7 Columbia-Suicide Severity Rating Scale (C-SSRS)**

The clinician will attend a certified rater training for the C-SSRS, to ensure consistent and accurate ratings.

The C-SSRS is a clinician-rated instrument that captures the occurrence, severity, and frequency of suicide-related ideations and behaviors during the assessment period. The C-SSRS must be administered by appropriately trained site personnel. Suicidal ideation is classified on a 5-item scale: 1 (wish to be dead), 2 (nonspecific active suicidal thoughts), 3 (active suicidal ideation with any methods [not plan] without intent to act), 4 (active suicidal ideation with some intent to act, without specific plan), and 5 (active suicidal ideation with specific plan and intent). The C-SSRS also captures information about the intensity of ideation, specifically the frequency, duration, controllability, deterrents, and reasons for the most severe types of ideation. Suicidal behavior is classified on a 5-item scale: 0 (no suicidal behavior), 1 (preparatory acts or behavior), 2 (aborted attempt), 3 (interrupted attempt), and 4 (actual attempt). More than 1 classification can be selected provided they represent separate episodes. For actual attempts only, the actual or potential lethality is classified for the initial, most lethal, and most recent attempts. C-SSRS assessments are presented in Appendix 3.

## **13 EFFICACY ASSESSMENTS**

### **13.1 ALS Functional Rating Scale**

The clinician will attend a certified rater training for the ALSFRS-R, to ensure consistent and accurate ratings.

The Investigator (or subinvestigator) will evaluate ALSFRS-R as presented in Appendix 1.

ALSFRS-R (Appendix 1) is a questionnaire used to measure the impact of ALS that is evaluated by the Investigator. The scale measures the subjects' physical function across 12 activities of daily living. The date of the evaluation along with the results will be recorded on the eCRF.

### **13.2 Time to Death, Tracheostomy, or Permanent Assisted Mechanical Ventilation**

On Day 1 of treatment with oral edaravone through EOT/ET, the Investigator (or subinvestigator) will investigate the presence or absence of the following events:

- Time (days) to death
- Time (days) to tracheostomy
- Time (days) to permanent assisted mechanical ventilation ( $\geq 23$  hours/day)

If any of the events are present, the following will be recorded in the eCRF: the date of the event and end of study date will be investigated. If the subject discontinues the study drug, study sites must follow-up with phone calls at Weeks 24, 48, 72, and 94 to determine if any of the above events have occurred (refer to Table 1). The evaluation results, together with the dates of the evaluation, will be recorded in the eCRF.

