**Figure 1: Study Schema**

Abbreviation: ET = early termination; EOT = end-of-treatment; EOS = end-of-study.

- Subjects will receive oral edaravone at a dose of 105 mg administered once daily for 10 days out of a 14-day period, followed by a 14-day drug-free period. The dose of edaravone should be taken following an overnight fast and at least 1 to 2 hours before the morning meal.
- Day 1 is equal to the Week 48 visit of the MT-1186-A01 study.

Table 1: Schedule of Assessments

Assessment	Open-label Treatment Period						Safety Follow-up Period a
	Week (window)	Day 1 (Based upon Week 48 procedures from 1186-A01)	12 (± 7D)	24 (± 7D)	36 (± 7D)	48 (± 7D)	
Cycle	1	4	7	10	13	16	19
Visit	1	2	3	4	5	6	7
Informed consent	X						
Eligibility criteria	X						
Demographics b	X						
Vital signs c	X	X	X	X	X	X	X
Orthostatic Vital Sign Assessment	X	X	X	X	X	X	X
Pregnancy test	X				X		X
Full Physical examination d1	X						X
Routine physical examination d2		X	X	X	X	X	
12-lead ECG e	X				X		X
Body weight	X	X	X	X	X	X	X
Time to event of death, Tracheostomy or permanent assisted mechanical ventilation f	X	X	X	X	X	X	X
Hematology g	X			X	X	X	X
Chemistry h	X			X	X	X	X
Urinalysis i	X			X	X	X	X

Assessment	Open-label Treatment Period								Safety Follow-up Period a
	Week (window)	Day 1 (Based upon Week 48 procedures from 1186-A01)	12 (± 7D)	24 (± 7D)	36 (± 7D)	48 (± 7D)	60 (± 7D)	72 (± 7D)	
Cycle	1	4	7	10	13	16	19	24	
Visit	1	2	3	4	5	6	7	8	9
Dispense edaravone j	X	X	X	X	X	X	X		
ALSFRS-R	X		X		X		X		X
C-SSRS	X		X		X		X		X
Medication Compliance Assessment k		X	X	X	X	X	X		
Adverse events	X	X	X	X	X	X	X		
Concomitant medications	X	X	X	X	X	X	X		X

Abbreviation: D = Day; ECG = Electrocardiogram; C-SSRS = Columbia-Suicide Severity Rating Scale; ALSFRS-R = Amyotrophic Lateral Sclerosis functional rating scale- revised; EOT = End-of-treatment; ET = early termination.

a. Subjects who withdraw from the study will complete the procedures listed in ET within 7 days of study discontinuation. If study treatment is discontinued, study sites must make all efforts to follow-up with phone calls.

b. Demographics will include age, sex, race, and ethnicity.

c. Vital signs will include systolic and diastolic blood pressure, heart rate, respiratory rate, and axillary, oral or tympanic body temperature (same method is to be used throughout the study).

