## 8 STUDY DESIGN

### 8.1 Overall Study Design

This is a Phase 3, international, multi-center, open-label, long-term extension study. The study will evaluate the safety of oral edaravone at a dose of 105 mg administered once daily for 10 days out of 14, followed by a 14-day drug-free period up to 96 weeks of treatment or until the drug is commercially available in that country.

Subjects who complete treatment in Study MT-1186-A01 and meet eligibility criteria will be enrolled into this open-label treatment study (MT-1186-A03) and will continue to receive oral edaravone, once daily, following an overnight fast, and subjects must continue to fast at least 1 to 2 hours before the next meal (e.g., breakfast). Treatment cycles will occur every 28 days (10 days on study drug out of a 14-day period, followed by 14 days off study drug).

Concomitant use of riluzole will be permitted during the study.

Subjects who discontinue from the study will complete the procedures listed in Week 96 (refer to Table 1 for further information) within 7 days of discontinuation.

Further details can be found in the Study Schema (Figure 1).

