## **9.6 Withdrawal of Individual Subjects**

A subject will be withdrawn from the study if the subject meets any of the following criteria:

- Requests to be withdrawn from the study;
- Has been found to be ineligible for participation in the study;
- The investigator (or subinvestigator) concludes that a subject should be withdrawn if continuation in the study is difficult due to AEs (e.g., hypersensitivity reactions);
- Is pregnant;
- Requires tracheostomy;
- Requires permanent assisted mechanical ventilation ( $\geq 23$  hours/day);
- The investigator (or subinvestigator) judges' continuation of the study to be inappropriate due to exacerbation of the primary disease;
- Development of significant liver dysfunction:
  - ALT or AST greater than 8 times the ULN;
  - Persistent ALT or AST of greater than 5 times the ULN for at least 2 weeks;
  - ALT or AST greater than 3 times the ULN AND elevated total bilirubin greater than 2 times ULN;
  - Symptoms consistent with liver dysfunction (e.g., fatigue, nausea, vomiting, abdominal pain/tenderness, fever, rash, eosinophilia  $>5\%$ ) with concomitant ALT or AST greater than 3 times the ULN.
- Note: Subjects meeting these criteria do not require withdrawal if alternative etiology is identified on discussion with the Study Medical Monitor.
- Noncompliance (i.e., misses more than 20% of doses in 2 consecutive dosing cycles, after consultation with MTDA or designee).

If a subject is withdrawn prematurely from the study, the date the subject is withdrawn from the study and the reason for withdrawal will be recorded in the electronic case report form (eCRF).

In the event that a subject drops out of the study at any time, the reason for discontinuation must be fully documented in the source documents and the eCRF. The Investigator site personnel will document the AEs and any other assessments in the source documents and will make every effort to complete all required early termination (ET) assessments. Study sites must make all efforts to follow-up with phone calls.

Subjects who are withdrawn from the study following enrollment may not re-enter the study.

The study may be terminated by the Sponsor at any time upon becoming aware of data that could compromise the safety and/or well-being of subjects or for any other reason it deems appropriate.

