#### **10.1.4 Unscheduled Visits**

An unscheduled visit is defined as any visit to the Investigator site outside of the protocol specified time points due to safety reasons or when a repeated measurement

is required (e.g., obvious measurement errors, measuring device failure, confirmation of out-of-range results), where the subject is seen by study personnel.

Due to COVID-19 restrictions related to site visits, safety assessments such as routine blood sampling or other assessments may be performed at the discretion of the Investigator and the site's abilities, including the performance of complete study visits in the subject's home or questionnaires via telephone. All assessments performed during the visits will be recorded in the eCRF.

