9.2.1. Efficacy Endpoints

For the efficacy endpoints, continuous data will be summarized at each analysis visit using summary statistics. Absolute values and changes from baseline will be presented. All categorical endpoints will be summarized at each analysis visit, using frequency tabulations. As the primary purpose of this study is to explore the safety of edaravone and not to perform confirmatory analyses, there will be no formal hypothesis testing performed and adjustments for multiplicity are not required.

9.2.1.1. ALSFRS-R change from baseline up to Week 96

The ALSFRS-R score of each item, domain score and total score will be listed. The total ALSFRS-R score and change from baseline to each post baseline visit up to week 96 will be plotted by visit. This analysis will be made on the safety analysis population.

The changes from baseline to (CHG) all post-baseline visits until week 96 in ALSFRS-R will be estimated using a Mixed Model for Repeated Measures (MMRM). The model includes response data from all post-baseline visits with no imputation for missing data. The ALSFRS-R at baseline (BASE), concomitant riluzole (RI) and visit (AVISIT) at week 24, 48, 72 and 96 will be included as fixed factors in the model. An unstructured covariance structure will be assumed and the denominator degrees of freedom will be computed using the Kenward-Roger method. In case the model will not converge with the unstructured covariance structure, the heterogeneous Toeplitz structure (TOEPH), Heterogeneous Autoregressive(1) (ARH(1)) , the heterogeneous compound symmetry (CSH), Toeplitz (TOEP), First-order autoregressive (AR(1)), and Compound symmetry (CS) will be used instead (in that order). The changes from baseline and their associated 95% Confidence Limits will be estimated, separately for each visit, from the same MMRM using LSMEANS estimates.

The SAS code planned for the analysis is outlined below.

[REDACTED]

For subgroup analysis, the above MMRM model will be employed using the corresponding subgroup categorical variable and the interaction between the subgroup and visit.

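### Subjects who stop study drug have no ALSFRS-R after the early-termination visit, although follow-up calls are already required, so the Week 96 decline is likely understated

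*Protocol*

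**What the plan says.** **Follow-up after stopping.** For subjects who have come off treatment, Protocol Section 13.2 states: "study sites must follow-up with phone calls at Weeks 24, 48, 72, and 94 to determine if any of the above events have occurred". Table 1, footnote a, adds: "If study treatment is discontinued, study sites must make all efforts to follow-up with phone calls". Neither place mentions ALSFRS-R.

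**Reasons for withdrawal.** Section 9.6 lists tracheostomy, the criterion "Requires permanent assisted mechanical ventilation", and an investigator's judgement finding "continuation of the study to be inappropriate due to exacerbation of the primary disease". It also lists reasons that need not reflect progression, such as the subject's request, pregnancy and non-compliance.

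**Last planned score.** Section 8.1 states: "Subjects who discontinue from the study will complete the procedures listed in Week 96", within 7 days. Those procedures include ALSFRS-R.

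**Analysis.** SAP Section 9.2.1.1 fits a mixed model for repeated measures (MMRM): "The model includes response data from all post-baseline visits with no imputation for missing data", with "visit (AVISIT) at week 24, 48, 72 and 96 will be included as fixed factors in the model". Protocol Section 17.3.5.1 and SAP Section 9.2.1 also plan descriptive summaries of change by visit. SAP Section 8.5 assigns an ET score to the closest scheduled visit, and only when that visit has no value. The SAP states no analysis under missing-not-at-random assumptions and no rule for ALSFRS-R after death.

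**Contrast with the event endpoint.** SAP Section 8.4.2.2 follows time to death, tracheostomy or permanent ventilation regardless of treatment status. ALSFRS-R has no matching rule.

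**The concern.** Part of the withdrawal process is driven by the same decline that ALSFRS-R measures. Subjects who leave for that reason contribute at most an ET score and nothing later, so the later visits describe a better-preserved group.

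An MMRM without imputation corrects for this only if, given the scores in the model, withdrawal does not depend on scores outside it. A subject who deteriorates after the last modelled visit and then leaves breaks that condition unless the ET score enters the model.

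ALSFRS-R change is the functional efficacy endpoint. SAP Section 2 says that the 96-week results will support publications and marketing, so an error towards slower decline would matter. The sites must in any case ring these subjects at Weeks 24, 48 and 72, which are ALSFRS-R weeks, and at Week 94, two weeks before the last one.

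**Working it through.** The documents state no ALSFRS-R slope, drop-out rate or expected Week 96 change, so the plan has no figure of its own to reproduce.

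**1. When does an ET score reach the model?** Inputs are the nominal days and windows in SAP Table 5 and the ET rule in SAP Section 8.5. Assumption: scheduled visits fall on their nominal days. An ET score can then fill a visit only if it lies in that visit's window before the nominal day. After that day the visit already has its own value.

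| Modelled visit | Nominal day | Window | ET days that can fill it | Count |
|---|---|---|---|---|
| Week 24 | 169 | 128–253 | 128–168 | 41 |
| Week 48 | 337 | 254–421 | 254–336 | 83 |
| Week 72 | 505 | 422–589 | 422–504 | 83 |
| Week 96 | 673 | 590–701 | 590–672 | 83 |

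- Usable days: 41 + 3 × 83 = 290. Possible ET days, Day 2 to Day 672: 671. 290 / 671 = 43%.
- Unused days: 126 in the Week 12 window (Day 2–127), which is not in the model, plus 3 × 85 = 255 on or after a filled visit. 126 + 255 = 381, and 290 + 381 = 671.
- If Week 12 is ignored because ALSFRS-R is not scheduled then, Days 85–168 (84 days) serve Week 24: 84 + 249 = 333, and 333 / 671 = 50%.
- These are shares of days. The share of subjects depends on when they leave.

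Example: a subject who leaves on Day 240 is closest to Week 24, which has its Day 169 value, so the ET score is not used. When an ET score is used, it can stand for a day up to 337 − 254 = 83 days later, which also makes the decline look smaller.

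**2. How large could the error be?** All inputs here are assumptions. The MMRM was approximated by maximum likelihood with an unstructured covariance, and deaths were ignored.

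*First set.* Mean slope −0.85 points per month (SD 0.55); 30% of subjects lose a further 0.9 per month from a random time; visit noise SD 1.8; about 38% drop-out, with log-odds rising by 0.1 to 0.3 per point lost since the last visit. True Week 96 change is about −22 points. Amount by which the estimate is too favourable:

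| Handling | MMRM | By-visit mean |
|---|---|---|
| ET score under the SAP 8.5 rule | about 0.5–1.0 | 0.9–2.6 |
| 60% of those who stop also scored later | about 0.2–0.4 | 0.3–0.9 |

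Leaving the ET score out altogether gives 0.9 to 2.8 points for the model. If every ET score filled the visit at which the subject dropped out, the model's error would be under 0.1. The ET rule therefore matters as much as the absence of later scores.

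*Second set.* Mean loss 0.8 or 1.0 points per four-week cycle over 24 cycles (true change −19.2 or −24.0), 30% or 50% withdrawn by Week 96, SAP ET rule applied:

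| Withdrawal driven by | MMRM too favourable by | By-visit mean too favourable by |
|---|---|---|
| Nothing related to decline | 0.2–0.4 | about 0 |
| Last observed score | 0.5–1.2 | 3.7–7.2 |
| Recent unscored decline | 2.1–4.8 | 4.4–8.6 |

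Scoring 60% of withdrawn subjects at the later weeks reduces the last MMRM range to about 0.8–1.5 (simulated without the ET score).

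**3. Would the existing calls fit the windows?** Week 94 is Day 94 × 7 + 1 = 659, inside the Week 96 window and 673 − 659 = 14 days from nominal. Calls at Weeks 24, 48 and 72 fall on the nominal days. Under the closest-value rule such a score would replace an earlier ET score in the same window.

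**The case against.** - **The decline that triggers withdrawal is meant to be scored.** This stands. A reader might infer that scores simply stop once fast decline leads to withdrawal. The documents do not support that, because an ALSFRS-R is planned within 7 days. What remains is that SAP Section 8.5 leaves many of those scores out of the model.
- **The MMRM may already be adequate.** If withdrawal depends on scores already in the model, most of the error is removed. This stands, and no document says which mechanism applies.
- **Not all exits reflect decline.** Treatment also ends when the drug becomes commercially available in a country (Protocol Section 10.1.2). Such exits are probably unrelated to decline and would dilute the error.
- **It is a choice of estimand.** The exploratory objective concerns 96 weeks of treatment, the study has one arm, and SAP Section 7.2 plans no hypothesis testing. Off-drug telephone scores would answer a somewhat different question and mix scoring modes. This is fair. Flagging the scores and reporting the model both ways meets it.
- **The telephone precedent is narrow.** Section 10.1.4 allows remote conduct, "including the performance of complete study visits in the subject's home or questionnaires via telephone", but because of COVID-19 restrictions and at the investigator's discretion. Section 10.1.1 does provide for telephone visits generally, though not for telephone ALSFRS-R.
- **A rater is needed.** Section 13.1 assigns the scale to the investigator or subinvestigator, and SAP Section 8.4.1.1 makes scoring by staff not trained for the study a major deviation. Whoever now makes the call may not qualify.
- **Calls may not cover everyone.** It is unclear whether repeated calls continue once a subject has had a tracheostomy or permanent ventilation. Severe progression in those subjects is already captured by the event endpoint.

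**Conclusion.** The gap is real: no ALSFRS-R is requested after the ET visit, withdrawal is partly tied to progression, and the SAP rule keeps an ET score on only about 43% of possible ET days (50% if Week 12 is ignored) when visits fall on nominal days. The Week 96 decline is likely understated, and the by-visit mean is more exposed than the MMRM.

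Under the first set of assumed inputs the model is too favourable by roughly 0.5 to 1 point. Across the second set the range is 0.2 to 4.8 points, depending mainly on whether withdrawal follows observed scores or recent unscored decline. These figures show direction and order of size only.

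A reader might infer that the reported decline is certainly too small, or too small by a known amount. The documents support neither. They give no slope, drop-out rate or withdrawal mechanism, and the target is undefined for subjects who die unless the SAP defines it. For an exploratory endpoint this is a cheap improvement and does not invalidate the study.

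**What to change.** **If data are still being collected.** In Protocol Section 13.2 and Table 1, footnote a, have a trained rater add ALSFRS-R to the calls at Weeks 24, 48, 72 and 94 for off-drug subjects who still agree to contact. State whether this includes subjects who have already had a tracheostomy or permanent ventilation. In SAP Sections 8.5 and 9.2.1.1, flag these scores as off-drug and telephone, report the MMRM with and without them, and state how death is handled.

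**If collection has closed.** This is possible, since SAP Section 8.4.1.1 already reports an outcome of the data review meeting. The SAP should at least let the discarded ET scores enter at their actual time, for example in a random-slope model. It should also add a missing-not-at-random sensitivity analysis, such as a delta adjustment, and state how death is handled.

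**Cost.** A protocol wording change, an eCRF page, a slightly longer call, a trained rater on that call, and mixed scoring mode for these subjects. Scores after death cannot be recovered. The SAP-only version needs no new data.

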## **14 STUDY DRUG TREATMENT**

### **14.1 Investigational Medicinal Product**

#### **14.1.1 Drug Product**

The Sponsor will provide edaravone oral suspension (21 mg/mL) in amber bottles, adapters, and oral syringes for each subject, for the duration of their participation in the study. Suspension bottles will contain approximately 1050 mg of edaravone in 50 mL for Cycles 1 through 24. The Investigator, a study nurse, the hospital pharmacy, or other appropriately qualified party, will dispense a sufficient quantity of edaravone bottles and ancillary kits consistent with each subject's daily dosage requirement and study visits according to the protocol.

Before administration, site staff, subjects, and caregivers must shake the bottle of study drug according to the dosing instructions and confirm no precipitation layer is on the bottom of bottle. Five mL (equivalent to 105 mg of edaravone) of the suspension will be administered to the subject by syringe.

